10.10.1 Toxicity Follow-up

Whenever a patient experiences toxicity that fulfills the criteria for a dose limiting toxicity (DLT) or serious adverse event (SAE), treatment with the study drug will be interrupted and the toxicity will be followed up. Patients whose treatment is interrupted or permanently discontinued due to a DLT, other adverse event, or clinically significant laboratory value, must be followed up at least once a week (or more frequently if clinically indicated) for 4 weeks, and subsequently at approximately 4 week intervals, until resolution or stabilization of the event, whichever comes first. Clinic visits may include physical examination, assessment of residual toxicity, and blood tests (including CBC and CMP). Appropriate clinical experts (such as cardiologists or dermatologists, etc) should be consulted as deemed necessary.

10.10.2 Dose Reductions and Dose Delays

For patients who do not tolerate the protocol-specified dosing schedule, dose adjustments are permitted in order to allow the patient to continue the study treatment. All dose modifications should be based on the worst preceding toxicity (NCI Common Toxicity Criteria, version 4.0).

Prior to completion of Cycle 1, treatment (either BYL719 or AI or both) can be held for up to 7 days for any reason, and then resumed at the same dose. After completion of Cycle 1,

treatment (either BYL719 or AI or both) can be held for up to 3 weeks for any reason, and then resumed at the same dose. The investigator may remove any patient from study for any toxicity if he/she believes that it is in the best interest of the patient to discontinue study treatment.

Inpatient dose reductions of BYL719 will not be allowed during Cycle 1 (within 28 days of starting study treatment), unless a DLT has occurred and been counted. This is in order to accurately determine the safe and tolerable dose of BYL719 when used in combination with letrozole or exemestane.

BYL719 dose modification guidelines for toxicities considered at least possibly related to the study treatment are outlined in Table 10-2 below. If a patient experiences unacceptable toxicity that fails to resolve after a maximum BYL719 dose delay of 21 consecutive days, then the patient should be discontinued from the study treatment. In exceptional situations, if the patient is clearly benefiting from the study treatment (i.e., stable disease, partial response, complete response), and in the opinion of the investigator no safety concerns are present, the patient may remain on the study treatment. Patients who discontinue from the study for a study-related adverse event or an abnormal laboratory value must be followed as described in Section 10.10.1.

For each patient, a maximum of two dose reductions (minimum dose of BYL719 for this study is 200mg daily on Arm A and Arm B, and 150mg intermittently on Arm C and Arm D) will be allowed after which the patient will be discontinued from the study treatment. Dose reduction for BYL719 means treatment at the next lower dose level of BYL719 (e.g., 300mg daily if the prior dose was 350mg daily, and 250mg daily if the prior dose was 300mg daily). In addition, a patient must discontinue treatment if, after treatment is resumed at a lower dose, the same toxicity reoccurs with the same or worse severity. If, after interruption of treatment and resolution, treatment is resumed at the same dose following the criteria in Table 10-2, and the same toxicity reoccurs with the same severity, next treatment re-initiation must resume at the next lower dose level irrespective of duration.

There will be no inpatient dose escalation for BYL719. For each patient, once a dose level reduction of BYL719 has occurred, the dose level may not be re-escalated during subsequent treatment cycles with the study drug.

There will be no dose escalation or dose reduction for letrozole or exemestane.

For specific guidelines related to hyperglycemia, see Section 10.10.3.

Table 10-2 Criteria for interruption and re-initiation BYL719 treatment

Recommended Dose Modifications for BYL719	
Worst Toxicity CTCAE v4.03 Grade (unless otherwise specified)	Recommended Dose Modifications any time during a cycle of therapy
BLOOD AND LYMPHATIC SYSTEM DISORDER	
Anemia	
Grade 1 (Hgb < LLN-10.0 g/dL)	Maintain dose level of BYL719.
Grade 2 (Hgb < 10.0 g/dL - 8.0 g/dL)	Maintain dose level of BYL719.

Recommended Dose Modifications for BYL719	
Worst Toxicity CTCAE v4.03 Grade (unless otherwise specified)	Recommended Dose Modifications any time during a cycle of therapy
Grade 3 (Hgb < 8.0 g/dL); transfusion indicated	Omit dose of BYL719 until resolved to CTCAE Grade ≤ 1 or baseline - If resolved in ≤ 14 days, then maintain dose level of BYL719. - If resolved in > 14 days, then ↓ 1 dose level ^a of BYL719.
Grade 4 (Life threatening consequences; urgent intervention indicated)	Discontinue study treatment.
ANC decreased (Neutropenia) Grade 1 (ANC < LLN - 1.5 x 10 ⁹ /L) Grade 2 (ANC < 1.5 - 1.0 x 10 ⁹ /L) Grade 3 (ANC < 1.0 - 0.5 x 10 ⁹ /L) Grade 4 (ANC < 0.5 x 10 ⁹ /L)	Maintain dose level of BYL719. Maintain dose level of BYL719. Omit dose of BYL719 until resolved to CTCAE Grade ≤ 1, then - If resolved in ≤ 7 days, then maintain dose level of BYL719. - If resolved in > 7 days, then ↓ 1 dose level ^a of BYL719. Omit dose of BYL719 until resolved to CTCAE ≤ Grade 1, then ↓ 1 dose level ^a of BYL719.
Febrile neutropenia Grade 3 (ANC < 1.0 x 10 ⁹ /L, single temperature of > 38.3°C or a sustained temperature of ≥ 38.0°C) Grade 4 Platelet count decreased (Thrombocytopenia) Grade 1 (PLT < LLN - 75 x 10 ⁹ /L) Grade 2 (PLT < 75 - 50 x 10 ⁹ /L) Grade 3 (PLT < 50 - 25 x 10 ⁹ /L) Grade 4 (PLT < 25 x 10 ⁹ /L)	Omit dose of BYL719, then - If resolved by ≤ 7 days, then ↓ 1 dose level ^a of BYL719. - If not resolved within 7 days discontinue patient from study treatment. Discontinue study treatment. Maintain dose level of BYL719. Maintain dose level of BYL719. Omit dose of BYL719 until resolved to CTCAE Grade ≤ 1, then - If resolved in ≤ 7 days, then maintain dose level of BYL719. - If resolved in > 7 days, then ↓ 1 dose level ^a of BYL719. Discontinue study treatment.
Bleeding Any bleeding (related to BYL719) resulting in platelet transfusion	Omit dose of BYL719 until no further bleeding has been observed. Continuation of study treatment may be considered.
CARDIAC DISORDERS	
QTcF > 500 ms (≥ Grade 3) or > 60 ms change from baseline on at least two separate ECGs	First Occurrence: -Interrupt BYL719 -Perform a repeat ECG within one hour of the first QTcF of > 500 ms or >60ms from baseline - If QTcF remains > 500 ms or >60ms from baseline, repeat ECG as clinically indicated until the QTcF returns to < 480 ms. -Seek cardiologist input; address electrolytes, calcium and magnesium abnormalities; concomitant medication must be reviewed. Once QTcF prolongation has resolved, BYL719 may be restarted at a one lower dose level Second Occurrence: Permanently discontinue BYL719 treatment
Cardiac disorders - others Grade 1 and 2	Maintain dose level of BYL719.

Recommended Dose Modifications for BYL719	
Worst Toxicity CTCAE v4.03 Grade (unless otherwise specified) Grade ≥ 3	Recommended Dose Modifications any time during a cycle of therapy Discontinue study treatment.
VASCULAR DISORDERS	
Hypertension Persistent hypertension CTCAE Grade 3 requiring more than one drug or more intensive therapy than previously Persistent hypertension CTCAE Grade 4 requiring more than one drug or more intensive therapy than previously	Omit dose of BYL719 until resolved to CTCAE Grade ≤ 1, then ↓ 1 dose level ^a of BYL719. Discontinue study treatment.
INVESTIGATIONS – RENAL	
Serum creatinine Grade 1 (> ULN - 1.5 x ULN) Grade 2 (> 1.5 - 3.0 x ULN) Grade ≥ 3 (> 3.0 x ULN)	Maintain dose level of BYL719. Omit dose of BYL719 until resolved to CTCAE Grade ≤ 1 or baseline, then - If resolved in ≤ 7 days, then maintain dose level of BYL719. - If resolved in > 7 days, then ↓ 1 dose level ^a of BYL719. Discontinue study treatment.
INVESTIGATIONS – HEPATIC	
Blood Bilirubin ^b (for patients with Gilbert Syndrome these dose modifications apply to changes in direct bilirubin only) Grade 1 (> ULN – 1.5 x ULN) Grade 2 (>1.5 – 3.0 x ULN) Grade ≥ 3 (> 3.0 x ULN)	Maintain dose level of BYL719. Omit dose of BYL719 until resolved to CTCAE Grade ≤ 1, then - If resolved in ≤ 7 days, then maintain dose level of BYL719. - If resolved in > 7 days, then ↓ 1 dose level ^a of BYL719. Discontinue study treatment. Note: If CTCAE Grade 3 or 4 hyper-bilirubinemia is due to the indirect (non-conjugated) component only, and hemolysis as the etiology has been ruled out as per institutional guidelines (e.g. review of peripheral blood smear and haptoglobin determination), then ↓ 1 dose level ^a of BYL719 and continue treatment at the discretion of the Investigator.
AST or ALT Grade 1 (> ULN - 3 x ULN) Grade 2 (> 3 - 5.0 x ULN) Grade 3 (> 5.0 - 20.0 x ULN) Grade 4 (> 20.0 x ULN)	Maintain dose level of BYL719. Maintain dose level of BYL719. Omit dose of BYL719 until resolved to CTCAE Grade ≤ 1 (or CTCAE Grade ≤ 2 in case of liver metastasis), then - If resolved in ≤ 7 days, then maintain dose level of BYL719. - If resolved in > 7 days, then ↓ 1 dose level ^a of BYL719. Note: If BYL719 is held for hepatic toxicity, then letrozole or exemestane should be also held until hepatic toxicity resolves to CTCAE ≤ Grade 1 (or CTCAE Grade ≤ 2 in case of liver metastasis). Discontinue study treatment.
METABOLISM AND NUTRITION DISORDERS	
Fasting Plasma Glucose	Please refer to the guidelines for study drug-induced hyperglycemia provided in Section 10.10.3

Recommended Dose Modifications for BYL719	
Worst Toxicity CTCAE v4.03 Grade (unless otherwise specified)	Recommended Dose Modifications any time during a cycle of therapy
Amylase and/or lipase elevation Grade 2 (> 1.5 - 2.0 x ULN) Grade 3 (> 2.0 - 5.0 x ULN) Grade 4 (> 5.0 x ULN)	Maintain dose level of BYL719. Omit dose of BYL719 until resolved to CTCAE Grade ≤ 2, then - If resolved in ≤ 7 days, maintain dose level of BYL719. - If resolved in > 7 days, then ↓ 1 dose level ^a of BYL719. Discontinue study treatment. Note: A CT scan or other imaging study to assess the pancreas, liver, and gallbladder must be performed within 1 week of the first occurrence of any CTCAE ≥ Grade 3 of amylase and/or lipase. If asymptomatic CTCAE Grade 2 elevations of lipase and/or amylase occur again at the reduced dose, patients will be discontinued permanently from study treatment.
NERVOUS SYSTEM DISORDERS	
Neurotoxicity Grade 1 Grade 2 Grade ≥ 3 or second occurrence of Grade 2	Maintain dose level of BYL719. Omit dose of BYL719 until resolved to CTCAE Grade ≤ 1, then resume treatment at the same dose level. Discontinue study treatment.
GI DISORDERS Pancreatitis Grade ≥ 3	Discontinue study treatment.
Diarrhea Grade 1 Grade 2 Grade 3 Grade 4	Maintain dose level of BYL719, but initiate anti-diarrhea treatment. Omit dose of BYL719 until resolved to CTCAE Grade ≤ 1, initiate anti-diarrhea treatment, then maintain dose level of BYL719. Omit dose of BYL719 until resolved to CTCAE Grade ≤ 1, initiate anti-diarrhea treatment, then - If resolved in ≤ 48 hours, maintain dose level of BYL719. - If resolved in > 48 hours, then ↓ 1 dose level ^a of BYL719. For 2nd occurrence of diarrhea CTCAE Grade 3 for > 48 hours despite the use of anti-diarrhea treatment, discontinue study treatment. Discontinue study treatment. Note: Antidiarrheal medication is recommended at the first sign of abdominal cramping, loose stools or overt diarrhea.
Nausea/Vomiting Grade 1 Grade 2 Grade 3 Grade 4	Maintain dose level of BYL719, but initiate anti-emetic treatment (see Section 9.6.1). Omit dose of BYL719 until resolved to CTCAE Grade ≤ 1, initiate anti-emetic treatment (see Section 9.6.1), then maintain dose level of BYL719. Omit dose of BYL719 until resolved to CTCAE Grade ≤ 1, initiate anti-emetic treatment (see Section 9.6.1), then - If resolved in ≤ 48 hours, maintain dose level of BYL719. - If resolved in > 48 hours, then ↓ 1 dose level ^a of BYL719. Discontinue study treatment.
SKIN and SUBCUTANEOUS DISORDERS	

Recommended Dose Modifications for BYL719	
Worst Toxicity CTCAE v4.03 Grade (unless otherwise specified) Rash/ photosensitivity	Recommended Dose Modifications any time during a cycle of therapy Please refer to the guidelines for study drug-induced hyperglycemia provided in Section 10.10.4

Recommended Dose Modifications for BYL719	
Worst Toxicity CTCAE v4.03 Grade (unless otherwise specified)	Recommended Dose Modifications any time during a cycle of therapy
GENERAL DISORDERS	
Fatigue Grade 1 or 2 Grade 3	Maintain dose level of BYL719. Omit dose of BYL719 until resolved to CTCAE Grade ≤ 1, then - If resolved in ≤ 7 days, maintain dose level of BYL719. - If resolved in > 7 days, discontinue patient from study treatment.
OTHER ADVERSE EVENTS	
Grade 1 or 2 Grade 3 Grade 4	Maintain dose level of BYL719. For intolerable grade 2 toxicity, may omit dose of BYL719 until resolved. Omit dose of BYL719 until resolved to CTCAE Grade ≤ 1, then ↓ dose level of BYL719. Discontinue study treatment. Note: These are general guidelines. The investigator may omit dose of BYL719, ↓ dose level of BYL719 or remove any patient from study for any toxicity, if he/she believes that it is in the best interest of the patient.

 All dose modifications should be based on the worst preceding toxicity. Once a dose has been reduced it will not be increased at a later time even if there is no toxicity. Patients who require more than two dose reductions of BYL719 will be discontinued from study drug treatment. If a patient requires a dose delay of > 21 consecutive days of BYL719 then the patient must be discontinued from the study treatment. Patients who discontinue from the study for a study-related adverse event or an abnormal laboratory value must be followed at least once a week for 4 weeks and subsequently at 4-week intervals, until resolution or stabilization of the event, whichever comes first, except specifically mentioned. For patients on either Arm C, receiving BYL719 on days 1-7 and 15-21 of a 28 day cycle, or arm D, receiving BYL719 on days 1-5, 8-12, 15-19, 22-26, omitted days will be counted from the date of decision to omit therapy. For example, for a patient on Arm C whose BYL719 is omitted at cycle 2 day 20, but whose toxicity resolves at cycle 2 day 27, therapy will be resumed at Cycle 3 day 1. That is, the study treatment calendar will continue unchanged regardless of treatment omissions. For a patient on Arm D whose BYL719 is omitted beginning cycle 2 day 15, but whose toxicity resolves at cycle 2 day 20, the patient will still not receive treatment on days 20 and 21 as per the unchanged study treatment calendar. Any issues arising in the setting of therapy held for toxicity will be discussed between the Principal Investigator and Novartis. 	

^a Dose reduction for BYL719 means treatment at the next lower dose level of BYL719 (e.g., 250mg daily if the prior dose was 300mg daily, and 200mg daily if the prior dose was 250mg daily).
 
^b Refers to total bilirubin
 
^c Refer to the guidelines for study drug-induced hyperglycemia provided in Section 10.10.3.
	

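### Section 10.10.2 omits *or worse* after a same-dose restart, so grade 2 diarrhea or nausea/vomiting that returns as a brief grade 3 need not be reduced, while a repeat grade 2 must be

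*Combined protocol and SAP*

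**What the plan says.** Section 10.10.2 (Dose Reductions and Dose Delays) has two recurrence rules in consecutive sentences.

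- Restart at a lower dose: the patient must stop treatment if "after treatment is resumed at a lower dose, the same toxicity reoccurs with the same or worse severity".
- Restart at the same dose after an interruption under Table 10-2: if treatment is resumed "and the same toxicity reoccurs with the same severity, next treatment re-initiation must resume at the next lower dose level irrespective of duration".

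Table 10-2 gives the actions by grade. For grade 2 diarrhea: "Omit dose of BYL719 until resolved to CTCAE Grade ≤ 1, initiate anti-diarrhea treatment, then maintain dose level of BYL719". Grade 2 nausea/vomiting is handled the same way, with anti-emetics. For grade 3 of either toxicity, BYL719 is omitted until grade 1 or lower, and then: "If resolved in ≤ 48 hours, maintain dose level of BYL719". If resolution takes longer than 48 hours, the dose drops one level. Grade 4 of either means discontinuation.

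The diarrhea entry has one recurrence line of its own: "For 2nd occurrence of diarrhea CTCAE Grade 3 for > 48 hours despite the use of anti-diarrhea treatment, discontinue study treatment". The nausea/vomiting entry has none.

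**The concern.** The first of the two sentences names both equal and worse recurrence; the second names only equal recurrence. A rule that forces a reduction when a toxicity returns at the same grade should do at least as much when it returns at a higher grade. Where the higher-grade row already reduces or discontinues, nothing is lost. Where that row allows a restart at full dose, the order of required actions is reversed.

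At stake is patient safety during continued treatment. A patient whose GI toxicity worsens on rechallenge could be rechallenged again at the same dose, with any reduction left to judgment. These toxicities are common with the drug: in the single-agent data in Section 3.5.2, treatment-related nausea of any grade occurred in 17 of 50 patients (34%), diarrhea in 16 of 50 (32%) and vomiting in 12 of 50 (24%). Those figures show why the rows matter; they do not estimate how often this particular sequence occurs.

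**Working it through.** No sample size, power or error rate is involved. The check follows the rules in Section 10.10.2 and Table 10-2 through each recurrence.

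**The GI path.** Start with grade 2 diarrhea or nausea/vomiting, held and restarted at the same dose, after Cycle 1.

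| Recurrence | Governing text | Required action |
|---|---|---|
| Grade 2 | Section 10.10.2, same severity | Reduce one level |
| Grade 3, resolved in ≤48 h | Grade 3 row (severity differs, so the 10.10.2 rule is not triggered) | Maintain dose |
| Grade 3, >48 h | Grade 3 row | Reduce one level |
| Grade 4 | Grade 4 row | Discontinue |

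The second line is out of order. By contrast, a brief grade 3 episode followed by another brief grade 3 episode does require reduction, because the severity is the same and duration is disregarded. The 48-hour allowance is thus withdrawn for an equal repeat but kept for a worsening one.

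**Does other text close the gap?**

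- "All dose modifications should be based on the worst preceding toxicity" points to the grade 3 row, which maintains the dose.
- The diarrhea recurrence line needs a second grade 3 episode lasting more than 48 hours.
- The note ending Table 10-2 lets the investigator reduce for any toxicity, but does not require it.

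**How far does it extend?** Twelve Table 10-2 entries allow a same-dose restart. Rank the actions maintain < reduce < discontinue, and compare the action for an equal recurrence with the action for each worse outcome in the table.

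| Entry | Same-dose restart after | Equal recurrence | Worse recurrence | Paths | Inverted |
|---|---|---|---|---|---|
| Anemia | Grade 3 | Reduce | Grade 4: discontinue | 1 | 0 |
| Neutropenia | Grade 3 | Reduce | Grade 4: reduce | 1 | 0 |
| Thrombocytopenia | Grade 3 | Reduce | Grade 4: discontinue | 1 | 0 |
| Creatinine | Grade 2 | Reduce | Grade ≥3: discontinue | 1 | 0 |
| Bilirubin | Grade 2 | Reduce | Grade ≥3: discontinue; indirect-only exception: reduce | 2 | 0 |
| AST/ALT | Grade 3 | Reduce | Grade 4: discontinue | 1 | 0 |
| Amylase/lipase | Grade 3 | Reduce | Grade 4: discontinue | 1 | 0 |
| Neurotoxicity | Grade 2 | Discontinue (own rule) | Grade ≥3: discontinue | 1 | 0 |
| Diarrhea | Grade 2, or grade 3 ≤48 h | Reduce | 2→3 ≤48 h: **maintain**; 2→3 >48 h: reduce; 2→4 and 3→4: discontinue | 4 | 1 |
| Nausea/vomiting | Grade 2, or grade 3 ≤48 h | Reduce | As for diarrhea | 4 | 1 |
| Fatigue | Grade 3 | At least reduce | No higher grade listed | 0 | 0 |
| Other adverse events | Intolerable grade 2 | Reduce | Grade 3: reduce; grade 4: discontinue | 2 | 0 |

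Total paths: 1+1+1+1+2+1+1+1+4+4+0+2 = 19. Inverted: 2. The other 17 require the same or a stricter action. The neurotoxicity entry shows the table can handle this: its discontinuation row reads "Grade ≥ 3 or second occurrence of Grade 2", so equal and worse recurrences are treated alike.

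Rash is not counted because Table 10-2 refers it to Section 10.10.4. There, grade 3 and intolerable grade 2 share a row, and a second occurrence carries a recommended reduction, so the action is not inverted.

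With *or worse* added and discontinuations kept, the two inverted paths become reductions, leaving 0 of 19.

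**The case against.** The strongest reply is that no clinician would read the rule this way. If an equal recurrence forces a reduction, a worse one does so all the more, and the preceding sentence shows what was meant. Table 10-2 is headed as recommendations, the investigator may reduce at any time, and issues with held therapy are to be discussed between the principal investigator and the manufacturer. Tolerating brief grade 3 GI toxicity is also deliberate: Table 9-2 counts it as a DLT only if it lasts at least 48 hours despite treatment.

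The inference is sensible, but it conflicts with an explicit instruction in the grade 3 row, and a mandatory safety rule should not depend on it. Discretion and discussion permit a reduction without requiring one. Accepting a first brief grade 3 episode does not justify treating a worsening repeat more leniently than an equal repeat.

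Several limits do stand:

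- The exposure is about one extra full-dose restart. If grade 3 returns after that, it is the same severity as the last episode and reduction is required.
- "Inpatient dose reductions of BYL719 will not be allowed during Cycle 1" unless a DLT has been counted, so the inversion arises mainly after Cycle 1.
- The path count describes the table; it does not measure patients affected.
- Accrual had closed at 51 patients by Amendment 13 (Section 1.0), so a correction helps only those still on treatment.

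**Conclusion.** The concern holds. Followed as written, Section 10.10.2 and Table 10-2 require less for a grade 2 GI toxicity that returns as grade 3 for 48 hours or less than for one that returns as grade 2. The defect is confined to two entries and 2 of 19 worse-recurrence paths. This rests on reading *same severity* literally as the same CTCAE grade, and on treating the Table 10-2 rows as the operative instruction when that rule is not triggered. The number of patients affected cannot be derived from the documents.

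The point is minor. It concerns a safety instruction and leaves the DLT definition, the dose-escalation decisions and the maximum-grade toxicity summary in Section 14.4 untouched.

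**What to change.** In the same-dose sentence of Section 10.10.2, extend the trigger to the same *or worse* severity and add at the end: *unless Table 10-2 requires discontinuation*. In the grade 3 rows for diarrhea and for nausea/vomiting, note that the 48-hour allowance to keep the dose applies only to a first occurrence, meaning no earlier interruption and same-dose restart for that toxicity. Grade 4 discontinuation, the discontinuation for a second prolonged grade 3 diarrhea episode, and the Cycle 1 bar on reductions stay as they are.

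The cost is a few words in one sentence and one note in each of two rows, with no change to assessments, sample size or analysis. The clinical price is that a patient on this path uses one of the two permitted reductions sooner. As with the existing rule for equal recurrence, there is no time limit between episodes; if the investigators want one, it should apply to both.

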10.10.3 Hyperglycemia Management

PI3K is a key component of the insulin signaling pathway. Therefore, hyperglycemia may be a marker of BYL719 activity on its intended target.

In the BYL719 single agent first-in-human study, hyperglycemia occurred in 24/50 patients (48%), in a dose-related fashion. At a dose of 270 mg daily, one patient experienced hyperglycemia CTCAE Grade 1, but no Grade 3/4 hyperglycemia was reported. At the MTD of 400mg daily, 10/16 (62%) of patients experienced hyperglycemia, among them 4 (25%) with Grade 3/4 hyperglycemia. In the majority of patients, hyperglycemia could be managed by administration of oral anti-diabetic drugs such as metformin or glimepiride. Occasionally treatment with insulin was required.

No hyperglycemia or related metabolic abnormalities have been noted in a large phase III studies of letrozole and exemestane.

Patients with controlled, non-insulin-dependent diabetes may be enrolled if fasting glucose <140mg/dL, even if currently requiring the use of anti-hyperglycemic agents (other than insulin). We are including these patients with well-controlled diabetes because we anticipate that they will be familiar with glucose management, and thus able to manage hyperglycemia associated with BYL719 potentially better than those patients without a prior diagnosis of diabetes.

Fasting glucose levels will be obtained at selected study visits during each cycle as shown in Table 10-1. For the purposes of dose delay decisions, glucose measurements should be in a fasted state, defined as a level obtained at least 8 hours after the most recent caloric intake.

Any patient experiencing hyperglycemia will be managed per the guidelines in the table below, and per standard medical practice for sequelae of hyperglycemia such as dehydration and acidosis.

Grade 4 hyperglycemia must be reported to the MSKCC IRB and Novartis. See Section 17.2 for reporting requirements.

Table 10.3 Hyperglycemia Management

- The below are guidelines that may be modified at the discretion of the Principal Investigator.
- Management of steroid-induced hyperglycemia and resultant decisions regarding dose-reduction are also at the discretion of the Principal Investigator.
- For any hyperglycemia \geq grade 1, if, upon recheck of the fasting plasma glucose, hyperglycemia is not present or is of a lower grade than the initial value, the patient should be managed as per guidelines for the more severe toxicity. For example, if a patient has a fasting glucose in the grade 2 range, and on recheck is grade 1, the patient should be managed as if she has a grade 2 toxicity. However, if the initial value would result in a DLT, and the repeat value is in a lower-grade range, determination of DLT is at the discretion of the Principal Investigator.
- Should a patient experience toxicity during the resolution of a prior, higher-grade toxicity, the patient should continue to be managed as per the guidelines for the higher-grade toxicity. For example, if the patient experiences grade 3 hyperglycemia on day 1, and this improves to a value within grade 2 hyperglycemia on day 5, the patient should continue being management as for grade 3 hyperglycemia rather than switch to management for grade 2 hyperglycemia.

Severity	Dose adjustment and management recommendations

Grade 1 (> ULN - 160 mg/dL) [> ULN - 8.9 mmol/L] confirmed within 48 hours
	
Continue BYL719 dosing and maintain the current dose level As per investigator's discretion, initiate or intensify medication with appropriate anti-diabetic treatment such as oral anti-hyperglycemic therapy (e.g. metformin) Check fasting glucose as clinically indicated and at least weekly for 8 weeks

Asymptomatic grade 2 (>160 - 250 mg/dL) [> 8.9 - 13.9 mmol/L]
	
Maintain dose level and re-check within 24 hours: if grade worsens or improves, follow specific recommendations; if grading is confirmed: Continue BYL719 dosing. Initiate or intensify medication with appropriate anti-diabetic treatment such as oral anti-hyperglycemic therapy (e.g. metformin) as per investigator's discretion; consider adding a second oral agent if no improvement after several days Monitor fasting glucose as clinically indicated and at least weekly until fasting glucose resolves to ≤ Grade 1 If fasting glucose does not resolve to ≤ Grade 1 within 14 days after institution of appropriate anti-diabetic treatment, reduce BYL719 by 1 dose level Continue with anti-diabetic treatment and check fasting glucose at least weekly for 8 weeks, then continue checking at least every 2 weeks


Asymptomatic grade 3 (> 250 - 500 mg/dL) [> 13.9 - 27.8 mmol/L]
 
Or Grade 2 with signs or symptoms of hyperglycemia (e.g., mental status changes, excessive thirst, polyuria)
	
Omit BYL719 and re-check within 24 hours: if grade worsens or improves, follow specific recommendations. If grading is confirmed: Omit BYL719 dosing. Consider administering intravenous hydration and intervention for electrolyte/ketoacidosis/hyperosmolar disturbances as clinically appropriate Initiate or intensify medication with appropriate anti-diabetic treatment (consider adding insulin) as per investigator's discretion. Monitor fasting glucose as clinically indicated and at least twice weekly until fasting glucose resolves to ≤ Grade 1 If fasting glucose resolves to Grade 1 within 14 days, then re-start BYL719 and reduce 1 dose level If fasting glucose doesn't resolve to Grade 1 within 14 days, then discontinue patient from BYL719 Continue with anti-diabetic treatment and check fasting glucose at least weekly for 8 weeks, then continue checking at least every 2 weeks

Grade 4 (> 500 mg/dL) [\geq 27.8 mmol/L]
 
Or Grade 3 with signs or symptoms of hyperglycemia (for ex., mental status changes, excessive thirst, polyuria)
	
Omit BYL719, initiate or intensify medication with appropriate anti-diabetic treatment (consider adding insulin), re-check within 24 hours. If grade improves then follow specific grade recommendations.
 
If fasting glucoses confirmed at Grade 4: Discontinue patient from BYL719

A diabetologist consultation should always be considered.
 
Based on current experience, hyperglycemia usually resolves within a few days after BYL719 omission; temporary omission of BYL719 may be considered as clinically indicated to improve control of hyperglycemia. Special attention should be paid to the risk of hypoglycemia in patients interrupting BYL719 treatment and receiving insulin or sulfonylurea.
 
For all grades : instruct patient to follow dietary guidelines according to local and/or institutional standards for management of diabetes mellitus (such as those provided by the American Diabetes Association) during the study
	

